## 7.0 ADVERSE EVENTS AND STUDY MONITORING

### 7.1 Definition of Adverse Events (AEs)

An AE is any unfavorable and unintended sign (including an abnormal laboratory finding), symptom, or diagnosis that occurs in a study participant during the conduct of the study REGARDLESS of the attribution (i.e., relationship of event to medical treatment/study product/device or procedure/intervention). This includes any occurrence that is new in onset or aggravated in severity or frequency from the baseline condition.

### 7.2 AE Collection Requirements for This Protocol

Post-entry, all AEs must be recorded on the eCRFs if any of the following criteria have been met.

- All Grade  $\geq 1$  AEs
- All suspected or confirmed irAEs
- All infusion reactions
- All AEs that led to a change in study intervention
- All AEs meeting SAE definition or Expedited Adverse Event (EAE) reporting requirement
- All targeted events listed in [section 6.3.4](#)

NOTE: SAEs or events meeting EAE reporting requirements should also be entered into the DAIDS Adverse Experience Reporting System (DAERS), an Internet-based reporting system. All SAEs, irAEs, and AESIs will be recorded in DAERS, regardless of causality.

All AEs that are reported must have their severity graded. To grade AEs, sites must refer to the Division of AIDS Table for Grading the Severity of Adult and Pediatric Adverse Events (DAIDS AE Grading Table), corrected Version 2.1, July 2017, which can be found on the DAIDS RSC website at <https://rsc.niaid.nih.gov/clinical-research-sites/daids-adverse-event-grading-tables>.

Infusion reactions, adrenal insufficiency, and pneumonitis should be graded per the National Cancer Institute's (NCI) Common Terminology Criteria for AEs (CTCAE) guidelines as outlined in [section 8.0](#), and can also be found in the National Cancer Institute's Table for CTCAE, version 5.0, found on the National Cancer Institute Web site:  
[https://ctep.cancer.gov/protocolDevelopment/electronic\\_applications/docs/CTCAE\\_v5\\_Quick\\_Reference\\_5x7.pdf](https://ctep.cancer.gov/protocolDevelopment/electronic_applications/docs/CTCAE_v5_Quick_Reference_5x7.pdf)

### Serious Adverse Events (SAEs)

A SAE is defined as any untoward medical occurrence that:

- Results in death.
- Is life-threatening.
- Requires inpatient hospitalization or prolongation of existing hospitalization.
- Results in persistent or significant disability/incapacity.
- Is a congenital anomaly/birth defect.
- Is an important medical event that may not be immediately life-threatening or result in death or hospitalization but may jeopardize the participant or may require intervention to prevent one of the other outcomes listed in the definition above.

### Adverse Events of Special Interest (AESI)

An AESI (serious or non-serious) is one of scientific and medical concern specific to the sponsor's product or program, for which ongoing monitoring and rapid communication by the investigator to the sponsor can be appropriate. Such an event might warrant further investigation in order to characterize and understand it. Depending on the nature of the event, rapid communication by the trial sponsor to other parties (e.g., regulators) might also be warranted.

AESIs include all cases of irAEs, felt to be related to study treatment, including:

- Grade 2 or greater infusion-related reactions
- Grade 2 or greater allergic/hypersensitivity reactions
- All irAEs regardless of grade, including but not limited to: dermatitis, pneumonitis, myocarditis, colitis, adrenal insufficiency/crisis, hypo- or hyperthyroidism, thyroiditis, diabetes, hypophysitis, hepatitis, systemic lupus erythematosus, nephritis, myasthenia gravis, and/or drug-induced liver injury (DILI)

For all AESIs, the core team should be contacted immediately via email at [[contact]](mailto:[contact]) (See [section 7.3.2](#)).

NOTE: Participants with an ongoing AESI at week 48, should be followed until the AE has resolved or stabilized in the opinion of the core team (see [section 6.2.4](#)).

### Infusion Reactions

Infusion reactions are defined as any AE that occurs during the infusion or within 24 hours after the infusion is completed. All infusion reactions must be reported as AEs and graded using the grading scales as instructed in [section 8.2](#).

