## 8.1 Toxicity

All AESIs must be reported and the study team notified within 24 hours of identification (see [sections 7.2, 7.3, and 8.0](#)), and include the following:

- Grade 2 or greater infusion-related reactions
- Grade 2 or greater allergic/hypersensitivity reactions
- All immune-related, treatment-related toxicities (irAEs) regardless of grade

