If a participant chooses to discontinue a cemiplimab/placebo infusion, the site should notify the A5370 core study team by email at [[contact]](mailto:[contact]) and encourage the participant to complete subsequent study visits until the end of the study. Refer to [section 6.2.5](#) for discontinuation evaluation instructions.

8.2.2 Grade 2: Moderate reaction; infusion interruption indicated but participant responds promptly to symptomatic treatment (e.g., antihistamines, NSAIDS, narcotics, IV fluids); prophylactic medications indicated for ≤24 hours.

For participants who develop a Grade 2 AE or toxicity during a cemiplimab/placebo infusion, the infusion should be stopped and the core study team must be notified within 24 hours by email at [[contact]](mailto:[contact]). Administer epinephrine, corticosteroids, IV antihistamines, bronchodilators, and/or supplemental oxygen as medically indicated. At the discretion of the site investigator, the infusion may be continued at 50% of the previous infusion rate once the adverse reaction has resolved or has decreased to Grade 1 in severity. Participant must be monitored closely for any recurrence or worsening or signs or symptoms. If the infusion reaction recurs at this rate of infusion, the rate may be further reduced, again at the discretion of the site investigator. The maximum time of infusion should not exceed 3 hours (180 minutes).

Participants who develop a Grade 2 AE or toxicity during a cemiplimab/placebo infusion may complete the infusion at the discretion of the site investigator, with careful monitoring. Grade 2 AEs that may be related to cemiplimab/placebo should be handled according to standard clinical practice and documented on the eCRF.

8.2.3 Grade 3: Prolonged reaction (participant not rapidly responsive to symptomatic medication and/or brief interruption of infusion) or recurrence of symptoms following initial improvement or hospitalization indicated for clinical sequelae

DISCONTINUE further doses of cemiplimab/placebo.

Participants who develop a Grade 3 AE or toxicity during a cemiplimab/placebo infusion should have infusion discontinued immediately and be disconnected from the infusion tubing. Administer epinephrine, corticosteroids, IV antihistamines, bronchodilators, and/or supplemental oxygen as medically indicated. No further study drug treatment should be administered. The core study team must be notified within 24 hours by email at [[contact]](mailto:[contact]).

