## 9.0 CRITERIA FOR DISCONTINUATION

### 9.1 Permanent and Premature Treatment Discontinuation

Study treatment is two single infusions of cemiplimab (anti-PD-1 antibody) or placebo. Study treatment should be discontinued for:

- Drug-related toxicity (see [section 8.1](#))
- A Grade 3 or 4 infusion reaction occurs (see [section 8.2](#))
- Discontinuation of ART
- Requirement for prohibited concomitant medications (see [section 5.4](#))
- Pregnancy or breastfeeding
- Request by participant to terminate treatment
- Clinical reasons believed life-threatening by the physician, even if not addressed in [section 8.1](#) of the protocol
- Positive results for antibodies to TPO, GAD65/GAD or islet cell antigen
- An irAE of any grade occurs
- Prolonged need (>7 days) for systemic steroids

NOTE A: Participants who receive one infusion but for whom treatment was discontinued prematurely will be followed on study off treatment per the schedule of events.

NOTE B: If the study participant experiences an irAE after the first infusion of cemiplimab/placebo at entry, study treatment should be discontinued (i.e., the participant would not receive the second infusion).

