#### 10.4.1 Safety

The criteria to be used to guide the SMC when determining dose resumption or dose escalation for each cohort are defined as not having observed:

- A. Three or more active-treated participants have experienced a Grade  $\geq 3$  AE that is related to study treatment (as judged by the core team, blinded to treatment arm and by the SMC who will receive unblinded data);
- B. Two or more active-treated participants have experienced an irAE (not including an infusion reaction AE) that is related to study treatment (as judged by the core team, blinded to treatment arm, and by the SMC who will receive unblinded data) as defined by:
  - i Grade  $\geq 1$  pneumonitis, adrenal insufficiency, myocarditis, diabetes, or uveitis;
  - ii Grade  $\geq 2$  colitis, myositis, rash, hyperthyroidism or hypothyroidism, or elevated AST or ALT.
- C. One or more active-treated participants have experienced a Grade  $\geq 4$  clinical AE (excluding asymptomatic laboratory abnormalities) that is related to study treatment (as judged by the core team, blinded to treatment and by the SMC who will receive unblinded data).

NOTE A: Asymptomatic Grade 4 laboratory abnormalities are addressed within A.

NOTE B: The following probability calculations assume a deterministic dose-escalation rule and do not reflect the essential element of SMC review and clinical consideration by the SMC of the data presented with respect to dose-escalation decisions.

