## 10.5 Data and Safety Monitoring

If at any time within a given dose cohort:

- a) Three or more participants experience a Grade  $\geq 3$  AE related to study treatment ([section 10.2.1.1](#)) (as judged by the core team, blinded to treatment arm); or
- b) Two or more participants experienced an irAE (not including an infusion reaction AE) ([see section 10.4.1B](#)) that is related to study treatment (as judged by the core team, blinded to treatment arm); or
- c) One or more participants experience a Grade 4 clinical AE or death and related to study treatment (as judged by the core team, blinded to treatment arm);

then enrollment into the study and treatment infusions will be temporarily suspended and the SMC, unblinded to treatment assignment, will be asked to review all safety data; review the relation to study treatment of the event(s) thought by the blinded core team to be a primary safety outcome; and recommend how the study should proceed with respect to resuming enrollment, continuing study treatment and dose escalation.

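### Infusion reactions are defined by timing alone and then excluded from the irAE count, so related low-grade irAEs can drop out; the endpoint status of a related Grade 2 infusion reaction is also contradictory

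*Protocol*

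**What the plan says.** **Definition.** Section 7.2, Infusion Reactions: "Infusion reactions are defined as any AE that occurs during the infusion or within 24 hours after the infusion is completed". Neither the type of event nor its relation to the infusion enters the definition.

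**Exclusion.** Escalation criterion B in 10.4.1 reads "Two or more active-treated participants have experienced an irAE (not including an infusion reaction AE) that is related to study treatment". It covers pneumonitis, adrenal insufficiency, myocarditis, diabetes and uveitis from Grade 1, and colitis, myositis, rash, thyroid disorder and raised AST or ALT from Grade 2. The pause rule in 10.5(b) uses the same exclusion: "Two or more participants experienced an irAE (not including an infusion reaction AE").

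**Class membership.** The AESI paragraph of 7.2 opens with "AESIs include all cases of irAEs, felt to be related to study treatment, including", and the first item beneath it is "Grade 2 or greater infusion-related reactions". Section 8.1 instead lists infusion-related reactions, allergic or hypersensitivity reactions and "All immune-related, treatment-related toxicities (irAEs) regardless of grade" side by side.

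**Primary outcome.** Section 10.2.1.1 counts a related Grade 3 or higher AE, or a related irAE of Grade 1 or higher. It does not mention infusion reactions.

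**Treatment.** Section 9.1 stops treatment when "An irAE of any grade occurs", and in a separate item for a Grade 3 or 4 infusion reaction. Section 8.2.2 says: "Participants who develop a Grade 2 AE or toxicity during a cemiplimab/placebo infusion may complete the infusion at the discretion of the site investigator".

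**The concern.** Two defects follow from this wording.

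First, an event can fit both definitions, and no section says which one prevails. Section 8.2 names rash as a sign of an infusion reaction, and 10.4.1(B) names Grade 2 rash as a countable irAE. A core team that applies 7.2 as written would class a related Grade 2 rash on the evening of an infusion as an infusion reaction and leave it out of the B count. The same holds for a late effect of the first dose that surfaces within 24 hours of the week 6 infusion. Rule B fires at two cases, so one excluded case can decide the outcome.

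Second, a related Grade 2 infusion reaction is an irAE under the AESI paragraph, and therefore a primary endpoint event under 10.2.1.1. Under 8.1 it is neither. This affects the primary safety rate. It may also affect replacement, because 6.2.5 waives replacement once the safety endpoint is met.

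**Working it through.** **1. Where the sections disagree on a related Grade 2 infusion reaction**

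| Section | Treated as an irAE? | Consequence |
|---|---|---|
| 7.2, AESI lead-in | Yes | Primary endpoint event through 10.2.1.1; stop through the any-grade irAE item in 9.1 |
| 7.2, AE collection list | No, separate items | None for the endpoint |
| 8.1 | No, parallel class | Not an endpoint event |
| 8.2.2 | Not addressed | Infusion may be completed |
| 9.1 | No, separate item | Stops only at Grade 3 or 4 |
| 10.4.1(B), 10.5(b) | Excluded from the count | Does not contribute |
| 10.2.1.1 | Silent | Depends on which class applies |

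The endpoint conflict is confined to Grade 2. Grade 1 reactions are not on the AESI list, and related Grade 3 or higher reactions are endpoint events on either reading. One disputed event in an arm of 12 is 1/12 = 8.3 percentage points.

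Replacement is affected only possibly. Sections 6.2.5 and 10.4 tie it to the safety endpoint, but 10.7 adds no enrolment slot when treatment stops for a treatment-related AE.

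**2. Which events leave the count**

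Criterion A (three participants with a related Grade 3 or higher AE) and criterion C (one with a related Grade 4 or higher clinical AE) carry no infusion-reaction exclusion. Nor do 10.5(a) and (c). Loss is therefore complete only for listed irAEs below Grade 3. A Grade 3 irAE moves from a threshold of two to a threshold of three.

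The grading scale can change as well: 8.2 grades infusion reactions on the CTCAE infusion-related scale, while 8.5 grades dermatitis by body surface area.

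**3. The protocol's own figures**

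Table 10.4.1-2 is exact binomial with n = 12: P(≥2) = 1 − (1−p)^12 − 12p(1−p)^11. For p = 0.1, 0.2, 0.3 this gives 0.341, 0.725, 0.915 (printed 0.34, 0.73, 0.91).

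Table 10.4.1-1 uses the model in 10.4.1, where Y is a Grade 3 or higher irAE, X a lower-grade B event and Z a Grade 3 or higher A event outside B, all independent given no C event:

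- X = (B−Y)/(1−Y) and Z = (A−Y)/(1−Y).
- P(escalate) = (1−C)^12 × P(at most two A and at most one B among 12).

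Pr(Y) is not printed, so it was varied from 0 to min(A, B). The acceptable example (0.03, 0.02, 0.01) gives 0.862-0.865 (printed 0.86). The unacceptable example (0.20, 0.20, 0.10) gives 0.043-0.078 (printed 0.06). Both agree with the table.

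**4. Sensitivity to the exclusion**

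Let f be the share of B events that fall in the 24-hour window and are dropped from B, with Grade 3 or higher events still counted under A. The documents give no value for f, so 0.10 to 0.50 is an assumed range. For the first two rows, replace p by p(1−f). For the last two, Pr(Y) is set at half of min(A, B); in the unacceptable example Y = 0.10 and X = Z = 0.10/0.90 = 0.111.

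| Quantity | f = 0 | 0.10 | 0.25 | 0.50 |
|---|---|---|---|---|
| P(≥2 counted irAEs of 12), p = 0.1 | 0.341 | 0.295 | 0.226 | 0.118 |
| P(≥2 counted irAEs of 12), p = 0.2 | 0.725 | 0.664 | 0.557 | 0.341 |
| P(escalate), unacceptable example | 0.061 | 0.071 | 0.087 | 0.117 |
| P(escalate), acceptable example | 0.863 | 0.866 | 0.871 | 0.877 |

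The exclusion can only lower the B count and raise the chance of escalation.

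**The case against.** The strongest reply is that the irAE label on infusion reactions rests on one loose lead-in. The third item under it covers all irAEs of any grade and would be redundant if the first item were already an irAE. The AE collection list, 8.1 and 9.1 keep the classes apart, and the irAE examples in 10.2.1.1 include no infusion reaction. On that reading the sections agree. This is probably what was meant, but the text says otherwise, and 10.2.1.1 lacks the exclusion that 10.4.1(B) and 10.5(b) needed.

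The second reply is that the drop-out route is narrow, and this stands. The onset times given are about 3.6 weeks for skin, 4 to 6 weeks for colitis and a median of 2.6 months for pneumonitis. Week 6 laboratory tests are drawn before the infusion (6.3.7), and a known or suspected irAE bars the second dose (6.3.5). What remains is mainly rash, or a clinical event that first appears just after the week 6 infusion.

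The third reply is that the SMC reviews all AEs and the criteria only guide it. That protects the escalation decision. It protects the pause less, because 10.5 is triggered by the blinded core team's counts before the SMC is asked to look, although 7.4 allows an interim review on any concern.

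A reader might also infer that an unrelated Grade 3 AE in the window forces a stop under 9.1. Section 8.0 rules this out: it mandates discontinuation criteria only for toxicities related to cemiplimab or placebo.

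**Conclusion.** The point holds for related events below Grade 3 in the irAE count, and for related Grade 2 infusion reactions in the primary endpoint. The protocol states a rule that misclassifies the first group and contradicts itself on the second.

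The size is probably modest. In the unacceptable example, escalation probability rises from about 0.06 to 0.07 if 10% of irAEs are excluded and to 0.12 if 50% are; the onset times make the upper part of that assumed range unlikely. For the endpoint, each disputed event moves an arm of 12 by 8.3 points.

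A reader might conclude that serious early irAEs escape the safety rules, or that a disputed event is nearly certain in this trial. Neither is supported: criteria A and C and their pause counterparts have no exclusion, and the documents give no rate for Grade 2 infusion reactions or for irAE onset within 24 hours. No printed probability is wrong.

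**What to change.** - **7.2, Infusion Reactions:** keep the 24-hour window, but limit the definition to events judged related to the infusion, with signs and symptoms as described in 8.2.
- **10.4.1(B) and 10.5(b):** state that the exclusion applies only to events the blinded core team judges to be infusion reactions rather than irAEs. An event judged to be an irAE listed in 10.4.1(B) then counts whatever its onset time. Do not tie this automatically to the case definitions in 8.0: they are unvalidated guidance and include urticarial rash, so a true infusion reaction could become an irAE and a stop under 9.1.
- **7.2, AESI lead-in:** list infusion-related reactions, allergic or hypersensitivity reactions and irAEs as three parallel classes, as 8.1 does.
- **10.2.1.1:** state whether related Grade 2 infusion reactions count, consistently with 10.4.1(B) and 10.5(b), and report them separately in either case.
- **Treatment:** the sponsor must reconcile 7.2, 8.2.2 and 9.1 on what follows a Grade 2 infusion reaction. No stopping rule is proposed here.

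The cost is a wording amendment to four sections plus that reconciliation. It needs no new data, visits or participants. Because it touches the primary outcome definition, it belongs in an amendment made while the core team is still blinded.

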## 7.3 Expedited Adverse Event (EAE) Reporting to DAIDS

### 7.3.1 Expedited Reporting of Adverse Events to DAIDS

Requirements, definitions, and methods for expedited reporting of AEs are outlined in Version 2.0 of the DAIDS EAE Manual, which is available on the RSC website at <https://rsc.niaid.nih.gov/clinical-research-sites/manual-expedited-reporting-adverse-events-daims>.

DAERS must be used for EAE reporting to DAIDS. In the event of system outages or technical difficulties, EAEs may be submitted using the DAIDS EAE Form. This form is available on the DAIDS RSC website at <https://rsc.niaid.nih.gov/clinical-research-sites/paper-eae-reporting>.

For questions about DAERS, please contact NIAID CRMS Support at [[contact]](mailto:[contact]). Please note that site queries may also be sent from within the DAERS application itself.

For questions about expedited reporting, please contact the DAIDS RSC Safety Office at [[contact]](mailto:[contact]).

### 7.3.2 Reporting Requirements for this Study

- The SAE Reporting Category, as defined in Version 2.0 of the DAIDS EAE Manual, will be used for this study.
- The study agents for which expedited reporting are required are: cemiplimab (anti-PD-1 mAb) and placebo for cemiplimab.
- In addition to the EAE Reporting Category identified above, other AEs that must be reported in an expedited manner are: All AESIs as noted in [section 7.2](#) felt related to study treatment.

If a particular sign/symptom is not specifically listed in the Division of AIDS Table for Grading the Severity of Adult and Pediatric Adverse Events, corrected Version 2.1, July 2017, refer to the Estimating Severity Grade section for the 'Clinical Adverse Events Not Otherwise Identified in the DAIDS AE Grading Table' grading scale.

NOTE: Possible DILI (or Hy's Law) is defined as any elevated ALT and/or AST of Grade 2 or greater ( $\geq 3 \times \text{ULN}$ ), alkaline phosphatase  $< 2 \times \text{ULN}$ , and an increase in bilirubin  $\geq 2 \times \text{ULN}$  with no other immediately apparent possible causes of AST or ALT elevation and hyperbilirubinemia (such as concomitant use of atazanavir), including, but not limited to, viral hepatitis, pre-existing chronic or acute liver disease, or the administration of other drug(s) known to be hepatotoxic.

AESI: All AESIs, serious and non-serious, must be reported using the same reporting process as for SAE reporting.

Other AEs that must be reported in an expedited manner (i.e., within 3 business days to the sponsor or designee) are as follows.

Pregnancy: Although pregnancy is not considered an AE, it is the responsibility of the investigator to report to the sponsor (or designee), within 3 business days of identification, any pregnancy occurring in a female or female partner of a male participant, during the study or within 26 weeks of the last dose of study drug.

Any complication of pregnancy affecting a female study participant or female partner of a male study participant, and/or fetus, and/or newborn that meets the SAE criteria must be reported as an SAE. Outcome for all pregnancies should be reported to the sponsor.

### 7.3.3 Grading Severity of Events

The Division of AIDS Table for Grading the Severity of Adult and Pediatric Adverse Events (DAIDS AE Grading Table), corrected Version 2.1, July 2017, must be used and is available on the DAIDS RSC website at <https://rsc.niaid.nih.gov/clinical-research-sites/daids-adverse-event-grading-tables>.

The grading system for suspected or confirmed infusion-related reactions, adrenal insufficiency, and pneumonitis is listed in [sections 8.2, 8.3.4, and 8.3.5](#), and can also be found in the National Cancer Institute's Table for CTCAE, version 5.0, found on the National Cancer Institute Web site: [https://ctep.cancer.gov/protocolDevelopment/electronic\\_applications/docs/CTCAE\\_v5\\_Quick\\_Reference\\_5x7.pdf](https://ctep.cancer.gov/protocolDevelopment/electronic_applications/docs/CTCAE_v5_Quick_Reference_5x7.pdf)

